### **End of Treatment (Week 8) – All participants**

Via phone contact 1-2 days prior to week 8. A maximum of three attempts should be made by the site personnel to contact the participant over the phone. Phone contact attempts must be within the visit window allowed per protocol. All attempts must be recorded in the source documents.

- Adverse Events
- Concomitant medication
- Adherence survey

In addition to the above the following assessments will be completed at week 8:

	Standard treatment monitoring group	Simplified treatment monitoring group
HOME	Completed at HOME by the participant: NIL	Completed at HOME by the participant: 
 
• Pregnancy test (females of child bearing potential only)
 

CLINIC	Completed at the CLINIC : 
 
• Vital signs and physical measurements
 
• HCV RNA (Local Lab.)
 
• LFTs, FBC and biochemistry (Local Lab.)
 
• Pregnancy test (females of child bearing potential only)
 
• Research specimen collection (Central Lab.): 
 
• EDTA plasma (at all sites)
 
 
 
	Completed at the CLINIC : NIL – participant is not required to attend the clinic

#### **SVR12 (week 20) - All participants**

- Vital signs and physical measurements
- Return study drug
- Health outcome survey (EQ-5D-3L)
- Participant Satisfaction survey
- HCV RNA (Local Lab.)
- LFTs, FBC and biochemistry (Local Lab.)
- Pregnancy test (females of child bearing potential only)
- Adverse Events
- Concomitant medication
- Research specimen collection (Central Lab.):
  - EDTA plasma (at all sites)
  - PBMCs (at selected sub-study sites only)

#### **Unscheduled visits**

Unscheduled visits may occur for a number of reasons including, but not limited to, adverse events, early treatment discontinuation or study termination. In the event of treatment or study termination an

unscheduled visit should be performed where possible. In the event of an unscheduled visit the following data may be collected if applicable:

- Adverse Events
- Concomitant medication
- Vital signs and physical measurements
- HCV RNA and genotype (Local Lab.)
- LFTs, FBC and biochemistry (Local Lab.)
- HIV antibody & HBV serology (Local Lab.)
- Pregnancy test (females of child bearing potential only)

## **6.2 Study Questionnaires**

All participants will undertake a number of study questionnaires at selected study visits as described below.

### **Adherence Survey**

Adherence to study drug will be assessed by a structured self-report adherence questionnaire completed at week 4 and EoT (week 8) by the participants with the nurse during the telephone contact visits.

### **Health Outcomes Survey (EQ-5D-3L)**

The EQ-5D-3L health questionnaire provides a simple descriptive profile and a single index value for health status. This information can then be translated into a health utility, which can be used for cost-effectiveness analyses. The EQ-5D-3L will be completed by all participants in the clinic at screening and SVR12 (week 20).

### **Participant Satisfaction Survey**

Participant satisfaction will be assessed via questionnaire completed by all participants at the screening visit and again following the completion to treatment at the SVR12 visit.

### **Practitioner Acceptability Questionnaire**

Acceptability of simplified HCV treatment monitoring will be assessed via study specific questionnaire completed by each site Principal Investigator and the primary Research Nurse prior to the commencement of screening and again following the completion of the SVR12 visit of the last patient at each site.

Practitioner Acceptability Questionnaire will not be completed on a per participant basis. It will only be completed by the practitioners twice during the study: before PPFV and after LPLV.

## **7.0 Recording and reporting Adverse Events (AEs) and Product Complaints**

### **7.1 Definitions of Adverse Events, Adverse Reactions and Serious Adverse Events**

#### **7.1.1 Adverse Event definition**

Adverse events and adverse drug reactions may occur in the course of this study and within the specified follow-up period. These events may also occur in screened participants during the screening period prior to enrolment as a result of protocol-specified interventions. Adverse events will be collected for all participants in the clinic at baseline and SVR (week 20) visits and via phone contact at the week 4 and EoT (week 8) visits.

The definition of an adverse event is any untoward medical occurrence in a participant administered with a pharmaceutical product which does not necessarily have a causal relationship with the product.

Pre-existing conditions or diseases that occur during the study (e.g. seasonal allergies, asthma or recurrent headaches) should not be considered as adverse events unless they change in frequency or severity

All adverse events encountered during treatment and for 12 weeks after drug discontinuation must be reported on the Adverse Event Page of the electronic case report form (eCRF).

Laboratory test abnormalities (results outside the normal range) as such should not be reported as adverse events unless they result in a clinically relevant condition including but not limited to modification or discontinuation of study drug. Overdoses of study drug without clinical sequelae should not be reported as an adverse event.

#### **7.1.2 Serious Adverse Event (SAE) (including Serious Adverse Drug Reactions)**

The Investigator shall report serious adverse events to the Kirby Institute and AbbVie within twenty-four (24) hours of learning of the event. In addition, the Investigator shall report to the Kirby Institute and AbbVie all pregnancies experienced by a Study subject within 24 hours of learning of the event.

A serious adverse event is defined as any event that results in any of the following:

- (i) death;
- (ii) a life threatening adverse event experience (i.e., participant was at immediate risk of death from the event as it occurred);
- (iii) a persistent or significant disability/incapacity;
- (iv) inpatient hospitalisation

- (v) prolongation of existing hospitalisation;
- (vi) a congenital anomaly/birth defect; or
- (vii) an important medical event that jeopardizes the participant and requires medical/surgical intervention to prevent one of the outcomes listed in (i) through (vii) of this definition.

## **7.2 Assessment of Adverse Events and Serious Adverse Events**

### **7.2.1 Assessment of Causality for Study Drugs and Procedures**

The investigator or designee must assess each adverse event for the following:

#### **Relationship**

- Unlikely: An adverse event that is unlikely to be related to the use of the drug or procedures.
- Possibly: An adverse event that might be related to the use of the drug or procedures.
- Probably: An adverse event that is likely to be related to the use of the drug or procedures.

### **7.2.2 Assessment of Severity**

The investigator or designee must assess each adverse event for the following:

#### **Severity**

- Mild: Discomfort noticed but no disruption of normal daily activity.
- Moderate: Discomfort sufficient to reduce or affect normal daily activity.
- Severe: Incapacitating with inability to work or perform normal daily activity.
- Life threatening: Represents an immediate threat to life.

## **7.3 Reporting Requirements**

### **7.3.1 Adverse Events**

All adverse events from the date of signing the consent form until twelve weeks after the last dose of study drug administration should be reported on the case report form. All clinically significant adverse events should be followed and recorded until its resolution (or stabilization in case it cannot resolve).

#### **Coding**

Adverse events will be assigned preferred terms and categorised into system organ classes according to the Medical Dictionary for Drug Regulatory Affairs (MedDRA) classification of the WHO terminology.

### 7.3.2 Serious Adverse Events

All serious adverse events (SAEs) should be reported within **24 HOURS** of becoming aware of the event to the Kirby Institute and AbbVie by email or fax on the Serious Adverse Event Reporting Form. The appropriate Serious Adverse Event form should be used. Reports should be followed promptly by detailed, written follow-up reports when all information is not included in the initial report. Follow-up reports should be reported within 24 HOURS also. The immediate and follow up reports should identify participants by unique code numbers assigned to study participants rather than personal identification. The investigator must also comply with all applicable ethical and regulatory requirement/s relating to the reporting of serious adverse events.

Any serious adverse event that is ongoing at the post-study follow-up visit must be followed until resolution or until the event stabilizes (for those events that will not resolve).

For deaths, the Principal Investigator will supply the sponsor and the IRB/IEC with any additional requested information (e.g. death certificate, autopsy reports and medical reports).

The Investigator shall make available to both the Kirby Institute and AbbVie promptly such records as may be necessary and pertinent to investigate any adverse event, if specifically requested by AbbVie.

SAE reports must be submitted to **BOTH the Kirby Institute AND AbbVie:**

**Kirby Institute:** Email: [[contact]](mailto:[contact])

[contact]

**AbbVie:** Email: [[contact]](mailto:[contact])

### 7.4 Suspected Unexpected Serious Adverse Reaction (SUSAR)

The Project Team in collaboration with the Medical Officer will review and identify all serious events which fit the criteria of a SUSAR and requiring expedited reporting to relevant parties.

The definition of a SUSAR is a serious adverse event which is both suspected as being related to the drug (i.e. has a reasonable suspected causal relationship and is unexpected) and where the nature and severity is not consistent with known information (e.g. the Investigator's Brochure).

The sponsor must expedite the reporting of all SUSARs to all concerned investigators/institutions, IRB/IEC/s, and regulatory authorities within the reporting timeframe. Reports must comply with the applicable regulatory requirements and ICH Guideline for Clinical Safety Data Management: Definitions and Standards for Expedited Reporting.

Researchers must inform the IRB/IEC and regulatory authorities of all SUSARs that occur during the study that may affect the conduct of the study or the safety of the participants or their willingness to continue participation in the study. Researchers must inform the IRB/IEC as soon as possible of any new information from other published or unpublished studies which may have an impact on the continued ethical acceptability of the study or which may indicate the need for amendments to the study protocol.

## 7.5 Product Complaints

All Product Complaints at any Study Site must be reported to both the Kirby Institute and AbbVie within twenty-four (24) hours.

**Kirby Institute:** Email: [[contact]](mailto:[contact])

[contact]

**AbbVie:** Email: [[name]](mailto:[contact])

*Product Complaint* means any suspected quality defect in the study drug or its package or labelling. Product Complaints may include, but are not limited to:

- (i) damaged or broken product or packaging issues;
- (ii) product appearance whose color/markings do not match the labeling;
- (iii) labeling discrepancies/inadequacies in the labeling/instructions;
- (iv) missing components/product.

## 8.0 Packaging, labelling, storage and accountability of clinical trial supplies

Glecaprevir/pibrentasvir will be provided by AbbVie and should be dispensed under the supervision of the investigator or a qualified member of the investigational staff, or by a hospital/clinic pharmacist.

All participants will be required to return the study drug to the site at the SVR12 visit. Returned study drug must not be dispensed again. Study drug may not be relabeled or reassigned for use by other participants.

A designated person at the study site must receive the study drug shipment. That person must check that the supplies are in good condition and are complete as per the shipping records. Study drugs must be stored in a secure location with limited access. The study drug must only be dispensed according to the protocol and records must be kept detailing supplies received, dispensed to the participant, returned from the participant and returned to the sponsor or destroyed at site, as applicable.

Study staff must not open and count clinical trial supplies prior to dispensing.

### **8.1 Formulation**

Glecaprevir and pibrentasvir are presented as a co-formulated, film-coated, immediate release tablet. The tablet strength is 100 mg glecaprevir and 40 mg pibrentasvir. The tablets are pink-colored, oblong biconvex shaped and debossed with “2nd” on one side.

The tablets do not contain gluten. The tablets contain lactose.

### **8.2 Packaging and labelling**

Glecaprevir/pibrentasvir 100mg/40mg tablets are packaged in bottles of 30 tablets. 3 bottles are required for 4 weeks of treatment, which includes an extra 2 days of treatment. 6 bottles are required for 8 weeks of treatment, which includes an extra 4 days of treatment.

### **8.3 Storage and handling**

Study drug should be stored in a securely locked area, accessible only to authorized site personnel. To ensure the stability of the study drug and to ensure proper product identification, the drug product should not be stored in a container other than the container in which they are supplied.

Glecaprevir/pibrentasvir should be stored between 15°C (59°F) and 25°C (77°F).

Care should be taken to ensure that the study drug is stored securely away from children and in dry conditions. The study drug should be kept in the original packaging.

### **8.4 Dosage and administration**

The study drug is to be administered orally once a day (three tablets per day) with food. Each participant must be given instructions to maintain approximately the same daily dosing interval between study drug doses. Participants should be instructed to swallow the study drug tablets whole. Participants should be instructed to only remove the tablets from the bottle immediately prior to dosing.

For a missed dose of study drug, participants should be instructed to take the missed dose of study drug as soon as possible during the same day. However, no more than the daily dose of glecaprevir/pibrentasvir should be taken on any calendar day. Participants should be cautioned never to double the next dose with a missed dose of study drug under any circumstances.

Participants in the standard arm will be dispensed with four-week supply (three bottles) at the Baseline and Week 4 visits.

Participants in the simplified arm will be dispensed with eight-week supply (6 bottles) at the Baseline visit.

## **9.0 Biological samples**

### **9.1 Laboratory supplies and sample processing**

Laboratory supplies for collection of research specimens (plasma, whole blood and PBMCs) will be supplied by the Kirby Institute.

The following blood samples will be collected as time point specified in the schedule of assessments:

- 10 mL EDTA plasma (20 mL at screening and baseline) for HCV RNA testing, virological factors associated with treatment clearance and future HCV related research;
- 4 mL EDTA whole blood for human genomic DNA analysis;
- 60 mL ACD plasma for PBMCs (sub-study sites only) for immunological factors associated with treatment clearance and future HCV related research;

Samples will be collected by sites and then processed and stored at -80°C (-200°C for PBMCs) at the site local laboratory for bulk shipment to the Kirby Institute laboratory. Detailed sample processing instructions will be provided in the Laboratory Manual.

EDTA plasma samples will be used for study endpoint analysis. HCV viral load will be measured using in-house and commercial assays. Sequencing of the viral genome will also be performed as a more accurate means of genotyping. Data generated from the sequencing may also be used to distinguish relapse from reinfection, to examine the prevalence of mixed infection and to look at factors associated with relapse including RASs.

PBMCs and whole blood samples may be used to examine host factors associated with viral clearance, including but not limited to HLA Type, IL28-B, ISG expression, IP-10 and other biomarkers.

### **9.2 Shipping of biological samples**

Samples must only be shipped to the Kirby Institute laboratory on the instruction from the SMART-C Project Coordinator.

It is the responsibility of each site Principal Investigator to ensure that all site staff handling, packaging, and/or shipping biological samples understand and comply with International Air Transport Association (IATA) regulations relating to the handling and shipping of hazardous goods and/or diagnostic specimens.

### **9.3 Future use of biological samples**

After the samples have been analyzed for the study endpoints as specified in the protocol, remaining samples will be stored for use in future Human Research Ethics Committee approved hepatitis C related research. Additional consent will not be sought for this storage and future use. It is not optional.

Participants not wishing to have their samples stored or used in future hepatitis C related research will not be eligible to participate in this study.

## **10.0 Statistics**

### **10.1 Sample Size**

The study is designed to enrol a total of 375 patients: 125 in the standard arm and 250 in the simplified arm. The primary efficacy endpoint of SVR12 will be assessed within each arm, and the primary comparison of SVR12 rates will be for non-inferiority of standard to simplified arms. With these patient numbers, the study has approximately 80% power to show non-inferiority to standard treatment monitoring with a lower confidence bound for the difference (standard – simplified) in SVR12 rates greater than –6% (assuming an SVR12 rate of 96% in both arms).

### **10.2 Assessments of efficacy**

A final full statistical analysis plan will be written and signed off by the Protocol Steering Committee prior to final study data lock.

#### ***Primary endpoints:***

1. SVR12 defined as the proportion of patients with undetectable HCV RNA at 12 weeks post end of treatment (week 20) based on ITT population.

#### ***Secondary endpoints:***

2. SVR12 defined as the proportion of patients with undetectable HCV RNA at 12 weeks post end of treatment (week 20) based on mITT population.
3. Proportion adherent to treatment and study visits (on-treatment adherence and early treatment discontinuation);
4. Change in health-related quality of life during treatment (measured by EG-5D-3L);
5. Resistance associated substitutions (RAS): SVR12 in participants with and without baseline RAS, and RAS distribution in participants with virological failures;
6. Patient treatment satisfaction measured by a questionnaire applied to all participants;

#### ***Exploratory endpoint:***

7. Provider acceptability of simplified monitoring strategy.

### **10.3 Efficacy analysis**

The primary analysis will compare the randomised treatment arms on an ITT basis (see section 10.4). The primary efficacy endpoint is the proportion of patients with undetectable HCV RNA at 12 weeks post end of treatment. The treatment arms will be considered non-inferior if the lower limit 95% CI of the difference between the two arms does not exceed -6%. There will be no extrapolation of data for the primary endpoint. Patients with missing data will be analysed as missing equals failure. Secondary analyses will compare randomised treatment groups based on available data (mITT Population).

For all secondary endpoints simple pairwise comparisons of the randomised treatment arms will be undertaken for both the ITT and mITT populations.

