### **10.5 Definition of Intent-to-treat Population**

Intent-to-treat (ITT) and modified intent-to-treat (mITT) populations will be used for efficacy analyses. All patients who receive at least one dose of study drug will be included in the ITT population (and safety population). The mITT population will exclude patients who have completed treatment (>95% adherence) (according to phone contact at week 8), but have not returned for their SVR12 assessment. The data from the ITT and mITT will be presented by the treatment arm assigned at the time of randomisation. For the primary analyses of non-inferiority tests, the percentage of patients achieving SVR12 in each arm will be calculated with confidence intervals (CI) using the normal approximation to the binomial distribution.

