#### **Modified Intention-To-Treat (mITT) Population**

The mITT population excludes participants who have completed treatment (>95% adherence) (according to phone contact at week 8), but have not attended follow up at post-treatment week 12.

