### **Secondary efficacy endpoints**

Secondary efficacy endpoints include:

- Proportion of participants achieving SVR12 in each arm (in the mITT, mITT-VF and per-protocol populations);
- Proportion of participants with virological failure;
- Proportion of participants who are adherent to treatment and study visits (on-treatment adherence and early treatment discontinuation);

For virological endpoints, the point estimates and 95% exact confidence intervals will be reported by study arm, by HCV genotype and by HIV serostatus.

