### **Adherence**

On-treatment adherence is recorded through self-reported adherence questionnaire at week 4 and week 8 (EoT) via phone contact visits, and by pill count at post-treatment week 12.

Study drug exposure and compliance will be summarised for all treated participants.

*On-treatment adherence* will be calculated by subtracting the number of missed doses from the total number of doses prescribed for therapy duration and dividing by the total number of doses prescribed for therapy duration. By pill count and self-reported questionnaire, compliance with glecaprevir/pibrentasvir will be individually calculated at the 90/90, 95/95 and 100/100 adherence levels, defined as receipt of  $\geq 90$ ,  $\geq 95$  or 100% of scheduled doses for  $\geq 90$ ,  $\geq 95$  or 100% of the scheduled treatment period, respectively.

A participant will be considered compliant if the individual receives  $\geq 95\%$  of scheduled doses for  $\geq 95\%$  of the scheduled treatment period. The percentage of compliant participants will be summarised for each arm and overall.

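### Protocol 10.3 adds an mITT comparison of adherence, discontinuation and visit attendance, although mITT membership depends on those same outcomes: a minor defect, because the ITT comparison is kept

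*Protocol*

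**What the plan says.** Protocol 10.3, on secondary endpoints: "For all secondary endpoints simple pairwise comparisons of the randomised treatment arms will be undertaken for both the ITT and mITT populations". The third endpoint listed in Protocol 10.2 is "Proportion adherent to treatment and study visits (on-treatment adherence and early treatment discontinuation"). Protocol 10.5 puts everyone who took at least one dose in the ITT set; the mITT set will "exclude patients who have completed treatment (>95% adherence) (according to phone contact at week 8), but have not returned for their SVR12 assessment". The SAP section on the mITT population uses the same rule.

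The SAP is narrower elsewhere. Under Secondary efficacy endpoints it names the restricted sets only for SVR12 ("Proportion of participants achieving SVR12 in each arm (in the mITT, mITT-VF and per-protocol populations")), and gives no set for adherence. Under Adherence it says: "Study drug exposure and compliance will be summarised for all treated participants". However, SAP Table 11 has rows for discontinuation and for loss to follow-up or missing SVR12 data, with columns for the arm difference, its 95% CI and P. Its footnote repeats the table in the mITT, mITT-VF and per-protocol sets.

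**The concern.** Everyone removed from mITT completed treatment, reported more than 95% adherence and did not return at week 20. These are components of the endpoint that 10.3 then asks to be compared in the remaining participants. Removal takes missed visits out of the numerator, and takes adherent completers out of the denominator for non-adherence and discontinuation.

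Attendance is the sensitive part. In the simplified arm, week 20 is the only scheduled clinic visit after baseline (Protocol 4.2), so poorer return is a plausible effect of the strategy. An mITT attendance comparison that looks balanced partly by construction could be taken as reassurance.

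**Working it through.** **Inputs.** From Protocol 10.1: 125 standard and 250 simplified participants, 96% SVR12 in both arms, margin 6 points, power about 80%. From Protocol 10.3: two-sided 95% CI, missing equals failure. Neither document gives a dropout or adherence rate, so all counts of missed visits and non-adherence below are assumptions.

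**The plan's own figure.** SE = √[0.96 × 0.04 × (1/125 + 1/250)] = 0.02147. Power = Φ(0.06/0.02147 − 1.96) = 79.8%, which agrees with the stated 80%. The design inputs are read correctly, and the power is not in dispute.

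**Week 20 attendance.** Assume 5/125 (4.0%) and 25/250 (10.0%) miss the visit. The ITT gap is 6.0 points (chi-square p = 0.043). The mITT rule removes those among them who are adherent completers:

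| Share of missers who are adherent completers | mITT missed, standard | mITT missed, simplified | Gap (points) | p |
|---|---|---|---|---|
| 100% | 0/120 | 0/225 | 0 | – |
| 80% | 1/121 (0.8%) | 5/230 (2.2%) | 1.3 | 0.35 |
| about 50% | 3/123 (2.4%) | 13/238 (5.5%) | 3.0 | 0.19 |

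A second set of assumed counts allows the share to differ by arm: adherent completers missing week 20 number 4 and 23, other missers 2 and 4. ITT attendance is 119/125 = 95.2% against 223/250 = 89.2% (−6.0 points). In mITT it is 119/121 = 98.3% against 223/227 = 98.2% (−0.1).

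Attenuation assumes broadly similar shares in the two arms. In the opposite extreme (all 5 standard missers adherent completers, none of the 25 simplified) mITT would show 0/120 against 25/250, a gap of 10.0 points. The direction is therefore not guaranteed.

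**Non-adherence and discontinuation.** Nobody removed discontinued or was non-adherent at the 95% level by the week 8 report. If a share m of an arm is removed, a rate q becomes q/(1 − m). The factor is 1.02 at m = 2%, 1.04 at 4% and 1.11 at 10%. If 96% SVR12 holds with missing equals failure, at most 4% of an arm can be missing, so the factor is at most 1/0.96 = 1.04.

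- Simplified arm better: 15/125 (12.0%) against 15/250 (6.0%), ITT difference −6.0 points, p = 0.043. Removing 0 and 10 gives 15/240 = 6.25%, difference −5.75, p = 0.058. Removing 0 and 25 gives 15/225 = 6.7%, difference −5.3, p = 0.088.
- Simplified arm worse: 13/125 (10.4%) against 50/250 (20.0%), ITT difference 9.6 points. Removing 0 and 25 gives 50/225 = 22.2%, difference 11.8.

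The rescaling can tip a borderline p-value. It cannot conceal a large difference, and it can exaggerate one.

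**What the primary analysis would show.** With 5/125 and 25/250 missing and no virological failure in either arm, ITT SVR12 is 96.0% against 90.0%. SE = √(0.96 × 0.04/125 + 0.90 × 0.10/250) = 0.0258, so the lower 95% limit is −6.0 − 1.96 × 2.58 = −11.1 points. A smaller gap, 3/125 and 16/250 missing (97.6% against 93.6%), gives SE 0.0207 and a lower limit of −8.1. Both lie below −6.

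**The case against.** A reader might infer that the plan hides a real arm difference in adherence or return. The documents do not support that.

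- The sentence in 10.3 requires the ITT comparison as well, and ITT is every dosed participant by randomised arm.
- SAP Tables 1 and 3 report follow-up completion and loss by arm without the mITT filter. Table 11 does so in ITT, with a difference and CI. Table 13 gives reasons for discontinuation by arm.
- Under missing equals failure, return problems of the sizes illustrated would already make the primary analysis miss its margin.

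It is also fair to say that week 20 attendance is not clearly the endpoint. The bracket in endpoint 3 names only on-treatment adherence and early discontinuation, and SAP Table 9 lists those two and no visit measure. Against that, study visits are named in the objective and the endpoint, and Protocol 5.2 has visit adherence recorded in the eCRF. That ambiguity calls for clarification.

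The overlap between mITT membership and drug adherence is incomplete. Membership rests on the week 8 telephone report, whereas the SAP also uses pill counts and 90%, 95% and 100% levels. Someone removed at 96% is not adherent at the 100% level. Pills are returned only at week 20, so those removed would generally have no pill count in either set.

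All of this stands and sets the size of the point. It does not make the mITT comparison of this endpoint informative. Nor does the SAP fully settle the matter: it departs from 10.3 without saying so, and the Table 11 footnote carries the same problem into planned outputs. In mITT the missing-data row loses every adherent completer who did not return. The discontinuation row is empty by definition in the per-protocol set. The mITT-VF set excludes all non-virologic failures, so both rows are empty there.

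**Conclusion.** The point holds as a minor defect. The additional mITT comparison of endpoint 3 is conditioned on its own outcome. For week 20 attendance, an assumed 6.0-point gap falls to between 0 and 3.0 points when the share of missers who are adherent completers is between all and about half, and similar in both arms. For non-adherence and discontinuation the effect is a rescaling by 1/(1 − m), at most 1.04 under the plan's SVR12 assumption and 1.11 at 10% removed, which can shrink or enlarge the arm difference. The counts are illustrative. The ITT comparison and the primary analysis are unaffected. What remains is one redundant, biased secondary result, an unreconciled difference between Protocol 10.3 and the SAP, and the Table 11 footnote.

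**What to change.** 1. State that mITT, mITT-VF and per-protocol comparisons are limited to SVR12 and virological outcomes.
2. State that treatment adherence, early discontinuation and study-visit attendance are compared between randomised arms only in the ITT (all-treated) set. Add visit attendance to the SAP Adherence section, saying which visits count.
3. Amend the SAP Table 11 footnote so that the discontinuation row and the row for loss to follow-up or missing SVR12 data are not compared between arms in mITT, mITT-VF or per-protocol.

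The cost is a few sentences and no new data; the analysis dropped is uninformative. Changing Protocol 10.3 itself is an amendment that needs ethics approval (Protocol 13.0). Protocol 10.2 leaves the full analysis plan to the SAP, signed off before data lock. A SAP statement that it supersedes 10.3 for these endpoints would therefore be the lighter route, with 10.3 aligned at the next amendment.
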